8.2.3 Intervention(s)

DORA uses a variety of AI technologies to deliver the patient follow-up call, including: speech transcription, natural language understanding, a machine-learning conversation model to enable contextual conversations, and speech generation. Together, these technologies cover the input, processing and analysis, and output needed to maintain a natural conversation. **DORA** is configured to deliver calls through a telephone connection as a real-time, stand-alone system: the operator inputs individual patient details to initiate the call and completes a summary in the electronic health record (EHR) afterwards. The call that patients will receive from **DORA** will include several conversational elements:

- Greeting and introduction
- Identification of patient
- Cataract follow-up questions
- Patient's queries
- (Decision)
- Questions about acceptability
- Closure of call

The entire conversation will be supervised by a clinician. This clinician will be able to interrupt the call at any point if the system fails, the patient struggles to interact with it, or **DORA** does not collect sufficient information from the patient. The call will proceed in the following stages (visualised in Figure 5):

- 1. Stage 1. Call initiation: the supervising clinician will confirm the suitability of the patient, input their details, and initiate the call.
- 2. Stage 2. Symptom assessment: Once the call has begun, **DORA** will verify the identity of the patient and proceed through the cataract follow-up questions. As the patient answers the questions, both **DORA** and the supervising clinician will record their independent assessment about the clinical significance of the symptoms elicited.
- 3. Stage 3. Management plan decision: Once all of the follow-up questions have been asked, **DORA** and the supervising clinician will independently make and record their decisions about the management plan for the patient. **DORA** will then inform the patient of the clinician's decision about their management plan (i.e. whether specialist review is required or not).
 - Stage 3a: Optionally, if required, the supervising clinician can ask additional clarifying questions.

Figure 5. Flow Diagram of DORA's call with patient

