8.2.4 Comparator(s)

Imperial sees all of their post-operative cataract patients at a face-to-face out-patient appointment with an ophthalmologist or specialist nurse. This is conducted between three to four weeks following the procedure. Therefore, patients at Imperial will receive their call from **DORA** within 3 days before their scheduled appointment (day 25-27 post-surgery). This will enable the results of the **DORA** call to be compared with the face-to-face appointment at Imperial to assess whether any complications were correctly identified and if the management plan remains the same.

For patients at both clinical sites, health records will be examined 90 days after the call to determine if the patient presented to an eye clinic with any complications from surgery. This comparison of the follow-up with actual complication rate will enable an assessment of **DORA's** safety (see Table 6).

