8.2.5.2 Secondary Outcomes

There will be several secondary outcome measures to assess the clinical safety, feasibility, usability, and acceptability of the system (see Table 6).

Clinical safety

To examine safety, two outcomes will be captured. Firstly, patients at both sites will have a retrospective case review of both general and ophthalmic electronic health records at 90 days after their initial operation. Complications will be identified from patient's medical records related to any unplanned eye-related clinical episode.

Secondly, all cataract surgery patients at Imperial were historically followed up face-to-face between 3-4 weeks post-surgery in a dedicated post-op clinic. Any complications requiring a change in patient management at slit lamp review or from attending eye casualty services (as the Oxford site does not normally perform face-to-face follow-ups) will be compared with the decisions made by **DORA** and the clinician. If Imperial changes their method of follow-up due to the COVID-19, assessment for complications will be done by checking hospital medical records as is done at the Oxford site.

Feasibility

Feasibility will be assessed by examining the proportion of autonomous calls that were completed without needing any intervention from the supervising clinician. All interruptions or clarifying questions of the supervised call will be logged; the supervising clinician will be asked to log the reason for asking clarifying questions. If clarifying questions were asked because the clinician felt that there was insufficient information for either individual symptoms or to make a management plan, the clinician's management plan before and after clarifying questions will be captured to see if clarifying questions changed the management plan.

Usability

Usability will be assessed using questions presented to patients following calls delivered by online and paper surveys distributed to participants. These questions will be drawn from the System

Usability Scale (SUS) and Telehealth Usability Questionnaire (TUQ; see 13.4 Appendix 4 for a sample survey) [14,15].

Acceptability, satisfaction, and appropriateness

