DORA's acceptability, satisfactoriness, and appropriateness will be assessed during qualitative interviews with a subset of the patients. These semi-structured interviews will provide an opportunity for patients to provide more in-depth feedback about what they liked about **DORA** and any barriers to use that they experienced during the call (see 13.5 Appendix 5 for a sample topic guide). The supervising clinician will also be asked to provide feedback about their level of satisfaction with the system and any safety concerns they might have.

Patients' willingness to recommend **DORA** to others will also be assessed at the end of the call [20]. **DORA** will calculate a net promoter score (NPS) by asking patients "on a scale of 1 to 10, how likely would you be to recommend this automated service to a friend or colleague." **DORA** will follow up by asking patients to "tell me why you gave that score."

Cost-effectiveness

Cost-effectiveness will be examined by collecting and analysing health economic data before and during the study. The costs of implementing **DORA** will be compared with historical data about the costs of the usual standard of care.

| Secondary Outcome | Outcome Measure | | | |
|-----------------------|---|--|--|--|
| Clinical Safety | Complications identified from patients' electronic health records up to 90 days following cataract surgery | | | |
| | Congruence between complications identified and management planned in DORA call and face-to-face follow up (Imperial) Comparison to data from patients attending eye casualty (Oxford) | | | |
| Feasibility | Proportion of autonomous calls that were completed without needing any intervention from the supervising clinician | | | |
| | Clinician-reported reasons for asking clarifying questions | | | |
| Usability | System Usability Scale (SUS) [14,17] | | | |
| | Telehealth Usability Questionnaire (TUQ) [15] | | | |
| | Qualitative feedback from semi-structured interviews | | | |
| Acceptability | Qualitative feedback from semi-structured interviews | | | |
| Satisfaction | Qualitative feedback from semi-structured interviews, Net Promoter Score (NPS) | | | |
| Appropriateness | Qualitative feedback from semi-structured interviews | | | |
| Cost-effectiveness | Comparison of the costs of implementing DORA and the costs of the usual standard of care | | | |
| Identify improvements | Synthesis of all of the outcome measures previously described | | | |

Table 6. Secondary Outcome Measurement

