8.4.2 Blinding

No blinding of participants will be done in the study, as all eligible patients will receive the same intervention. The clinicians listening to the call will be blinded to **DORA's** decisions when they are making their own assessments.

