8.4.3 Methods of Data Collection

8.4.3.1 Quantitative data collection

The key data to be collected are **DORA** and the clinician's decisions. This will include data on symptoms as well as an overall assessment. Both **DORA** and the clinician will separately record their decisions about symptoms, clinical assessment, and management plan. **DORA** will record the decisions in the **DORA** database, which will be accessed by the study team during the evaluation to compare against the clinician decisions. Usability of the system will be assessed using the SUS and

TUQ questionnaires (see 13.4 Appendix 4). These will be delivered to all participants shortly after they have had the call with **DORA** via an online or paper survey (see Figure 6).

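### Nothing masks the clinician at the Imperial face-to-face visit to the call result, so the Table 6 congruence measure could be inflated (low priority, cheap to fix)

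*Protocol*

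**What the plan says.** Protocol 8.2.4 has Imperial patients called within 3 days before a routine visit with an ophthalmologist or specialist nurse. The call is then compared with the "face-to-face appointment at Imperial to assess whether any complications were correctly identified and if the management plan remains the same".

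Protocol 8.2.5.2 defines what the visit contributes: "Any complications requiring a change in patient management at slit lamp review or from attending eye casualty services" is compared with the decisions of both DORA and the clinician. Table 6 lists the resulting measure as "Congruence between complications identified and management planned in DORA call and face-to-face follow up (Imperial" site).

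Two statements deal with masking. Section 8.2.5.1 masks DORA and the supervising clinician to each other. Section 8.4.2 adds: "The clinicians listening to the call will be blinded to" DORA's decisions. Neither mentions the person who conducts the visit. The limitations in 8.6 and the SAP do not raise the matter.

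Section 8.2.3 describes what happens to the call result. The operator "completes a summary in the electronic health record (EHR) afterwards", and DORA will "then inform the patient of the clinician's decision about their management plan". DORA's own decisions go to a separate database (8.4.3.1), "which will be accessed by the study team during the evaluation to compare against the clinician decisions".

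**The concern.** When one assessment is used to check another, the second should be made without knowledge of the first. Here the call comes first and its result already exists when the patient is seen. A visit clinician who knows that the patient passed a check a day or two earlier may be readier to leave the plan alone. One who knows that review was advised may look harder or act sooner. Either response moves the visit towards the call.

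What is at stake is one secondary safety measure at one site, but a useful one. The supervising clinician hears the same call as DORA, so both can miss what the call does not bring out. Oxford has no routine visit, and the 90-day review depends on patients presenting. The Imperial visit is the only planned in-person examination of patients whatever the call decided.

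**Working it through.** The plan gives no figure for this measure, so there is none to reproduce. The check is a comparison of sections, followed by short algebra on direction.

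**1. Is the visit a check on the call?** Yes: 8.2.4, 8.2.5.2 and Table 6 all say so.

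**2. Is the visit clinician masked?** No provision in the Protocol or SAP covers this person. Sections 8.2.5.1 and 8.4.2 concern the call only.

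**3. Can the call result reach the visit?** There are two open routes, both in 8.2.3: the health-record summary and the patient. The patient is told the supervising clinician's decision, not DORA's. The content and readers of the summary are not stated. So the supervising clinician's decision can travel. DORA's decision travels only where the two agree or where the summary includes it.

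**4. Which part of the visit is exposed?** The visit event combines a finding and a decision: a complication, and the judgement that it requires a change of management. The slit-lamp finding is fairly objective. The decision is more open to influence.

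**5. Direction for congruence with the supervising clinician.** Treat the plan as the two-way choice of 8.2.5.1. Let D be the share of patients whose visit plan, made without knowledge of the call, would differ from the supervising clinician's. Let w be the share of those swayed to match.

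- Congruence without sway: 1 − D
- Congruence with sway: 1 − D(1 − w)
- Change: + wD

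Under sway towards the supervising clinician's decision, this cannot fall, and it cannot rise by more than D. The documents give neither D nor w.

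**6. Direction for congruence with DORA.** Split D into A, where DORA sided with the supervising clinician, and B, where DORA sided with what the visit would have found. With the same w in both parts, sway adds wA agreements and removes wB.

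- Change: w(A − B)

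This is upward when A exceeds B. If DORA and the supervising clinician always agree, B = 0 and the full wD carries over. The more they disagree in these patients, the smaller the rise, and it can reverse.

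**7. Direction for DORA's sensitivity, if it were computed against the visit event.** Let s be the true sensitivity. Let o be the share of DORA's misses that the supervising clinician also passed, and q the share of DORA's detections that the supervising clinician passed. Let d be the share of passed complications that the visit then does not record as a change.

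- Apparent sensitivity: s(1 − qd) / [s(1 − qd) + (1 − s)(1 − od)]

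This exceeds s only when o is greater than q. That is likely, because DORA and the supervising clinician judge the same conversation, but the documents do not guarantee it.

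**8. What is untouched?** The primary kappa compares DORA with the masked supervising clinician (8.5.1). The baseline sensitivity and specificity in 8.5.1 are defined from hospital records over 90 days. Neither is claimed here to depend on the visit.

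**The case against.** The strongest reply has four parts.

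- **The leak is hypothetical.** No section says that the visit clinician reads the summary. This stands, and is why the claim is only that congruence could be inflated. But nothing prevents it either, and the patient is told the decision.
- **Slit-lamp findings are hard to sway.** In the Imperial audit (Appendix 6) all seven complications needing a management change were uveitis (six) or cystoid macular oedema (one), and each patient was given maxidex. Such findings come from examination, not from a five-symptom call. This largely stands for detection. It stands less well for the plan: four of the six uveitis patients were treated and discharged, and whether to treat or change the plan is still a decision.
- **The visit is routine care.** It takes place whether or not the patient is in the study, so instructions to clinic staff have a cost. This stands and limits what is reasonable to ask.
- **The measure is minor.** It is one secondary measure at one site, in a study seeking preliminary evidence. This stands and sets the priority.

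A reader might also infer that the SAP's `unexpected-change-management` variable is the visit result, so that the SAP's sensitivity against it is biased. The documents do not support that. The SAP does not give the variable's source, and its table columns are headed as a 3-month audit, which points first to the record review.

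**Conclusion.** The gap is real and narrow. The Imperial visit checks the call, its clinician is not masked, and two routes for the supervising clinician's decision are open. Visit-versus-clinician congruence on the management plan could be inflated, and visit-versus-DORA congruence to the extent that DORA and the supervising clinician agree. This assumes that the result does reach the visit clinician and pulls the plan towards it. The size is unknown.

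Three stronger readings should be resisted. First, a reader might conclude that DORA's sensitivity must be biased upward; step 7 shows that this is likely but not assured. Second, a reader might take DORA's own decision to be what leaks; the text shows a route only for the supervising clinician's. Third, a reader might extend the point to the primary kappa or to the 90-day sensitivity and specificity; neither is challenged.

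The point also lapses if face-to-face visits end: "If Imperial changes their method of follow-up due to the COVID-19, assessment for complications will be done by checking hospital medical records". It is a cheap improvement of low priority.

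**What to change.** **Protocol 8.4.2.** While Imperial keeps face-to-face visits, add that the visit clinician records slit-lamp findings and management plan before opening the call summary, then reads the summary in the same visit and logs any later change of plan separately. Use the first record for the Table 6 congruence measure. No clinical information is withheld from care.

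**SAP.** State the source of `unexpected-change-management`. For the visit-based congruence measure, do not count patients who miss the visit as having no change; the Imperial audit had 24 of 25 attending. Apply the same rule to `unexpected-change-management` only if it is drawn solely from the visit. If it is a record-audit item, the rule would wrongly drop patients with valid 90-day records.

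**Cost.** One sentence in the Protocol, a few lines in the SAP, and one extra recording step and data field in a routine clinic whose ophthalmologists and nurses must be told of it. No extra visit is needed. Masking stays partial, because patients may mention the result; recording first deals only with the health-record route.

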8.2.5 Outcomes

8.2.5.1 Primary Outcomes

Agreement

The primary outcome of the study is to establish preliminary safety evidence by evaluating the level of agreement between **DORA** and the expert human clinician on symptom and overall management plan decisions.

To evaluate agreement, **DORA's** ability to classify five key symptoms from the conversation will be compared with a supervising clinician's classification of the same five symptoms: redness, pain, reduced vision, flashing lights, and floaters (see Table 5). For this study, the supervising clinician's decision - made based on the information from the call with **DORA's** decision masked - is considered the gold-standard for evaluation. Both **DORA** and the supervising clinician (masked to each other) will independently indicate for each symptom, whether the symptom is:

- 1. Absent (e.g. no pain)
- 2. Present but not clinically significant (e.g. mild gritty sensation)
- 3. Present and clinically significant (e.g. deep and persistent pain)
- 4. Insufficient information for classification

The agreement between **DORA** and the clinician on the patient's management plan will be evaluated in the same way as the symptoms. **DORA** and the clinician will independently select one of the following options for the patient's management plan:

- 1. Passes check (patient continues to next step of their care as planned, e.g., Discharge from hospital care, add to waiting list for second eye surgery, or continue routine follow-up in clinic for another ophthalmic condition)
- 2. Needs clinical assessment relating to the cataract surgery

Ability to gather sufficient information

To evaluate **DORA's** ability to gather enough information for a clinician to decide a patient's management plan and the necessity for the clinician to ask clarifying questions will be assessed. If clarifying points are necessary for the clinician to make a decision, the clinician will ask the necessary questions, and then document updated assessments for symptoms and overall management (see Figure 5). Either 12 or 18 data points will be collected from each call depending on if clarifying questions are asked.

• Every Conversation

- o 5 symptom decisions from DORA + 1 clinical decision from DORA
- o 5 symptom decisions from Clinician + 1 management plan from Clinician
- If clarifying questions asked
 - Post-clarification 5 symptom decisions from Clinician + 1 management plan from Clinician

This will allow us to test the hypothesis that clarifying questions affect the clinical management plans (see Table 5).

| Primary Outcome | Outcome Measure |
|-----------------|---|
| Agreement | Whether or not the clinician had to interrupt the call to ask clarifying questions Inter-rater reliability: the degree of agreement between DORA and the clinician on their assessments of the individual symptoms and the management plan |

Table 5. Primary Outcome Measurement

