A Clinical Investigation of an Autonomous Phone Conversational Agent for Cataract Surgery Follow-up

NCT05213390

30 August 2022

Statistical analysis plan

Using the variables:

- doraoutcomeupdate (0 = pass, no review, 1 = fail, needs review)
- supervisoroutcomeupdate (0 = pass, no review, 1 = fail, needs review)

Primary outcome: Agreement between Dora and clinician for overall outcome decision and each symptom (x5)

- Inter-rater reliability (kappa)
- Accuracy (%)
- Data regarding true/false negatives/positives

	Clinician: follow-up (1)	Clinician: no follow-up (0)
Dora: follow-up (1)	ТР	FP
Dora: no follow-up (0)	FN	TN

• Sensitivity, specificity, AUC

Secondary outcomes

Clinical safety: Comparison with real complication rate

*Note: please do this analysis three times, once for each of the three complication measures
Data regarding true/false negatives/positives (Tables 2-3)

	Complications: 3 month audit	No complications: 3 month audit
Dora: follow-up	ТР	FP
Dora: no follow-up	FN	TN

- Sensitivity, specificity, AUC
- Variables
 - Dora follow up: "doraoutcomeupdate"
 - Complications:
 - "hospital-review-within-3-months"
 - 0 = no hospital review, 1 = hospital review
 - "unexpected-change-management"
 - 0 = no unexpected change management, 1 = unexpected change management

EUR ING [name] MA MSc MBA MPA PhD CEng FBCS Associate Professor of eHealth

"unplanned-hospital-rev"

• 0 = no hospital review, 1 = hospital review

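### The clinician's first management plan has no code for too little information to decide, so the before/after clarification comparison contains forced entries in the calls it is meant to study

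*Protocol*

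**What the plan says.** Protocol 8.2.5.1 gives each of the five symptoms four categories, the last being "Insufficient information for classification". It says the management plan is assessed in the same manner as the symptoms, yet for the plan DORA and "the clinician will independently select one of the following options", and the list ends at the second option, "Needs clinical assessment relating to the cataract surgery".

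The same section requires, in every conversation, "5 symptom decisions from Clinician + 1 management plan from Clinician", and a second clinician set if clarifying questions are asked. Section 8.2.3 has the same order: the plan is recorded at Stage 3, and clarification is the optional Stage 3a.

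The protocol expects that some clinicians will be unable to decide. Section 8.2.5.1 opens the clarification route with "If clarifying points are necessary for the clinician to make a decision". Section 8.2.5.2 (Feasibility) names as a reason "insufficient information for either individual symptoms or to make a management plan", asks for the reason to be logged, and says that in such calls the plan is captured before and after. The text just above Table 5 states the hypothesis that clarifying questions affect management plans.

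The SAP codes the clinician's overall decision as "supervisoroutcomeupdate (0 = pass, no review, 1 = fail, needs review", with no third value and no definition of the variable. It contains no clarification analysis.

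**The concern.** When clarification is requested because no plan can yet be made, there is no real plan to record beforehand. The form still demands one, and neither document says how to complete it. A move from undecided to pass is then stored as no change if the clinician had entered pass, and as a change if the clinician had entered needs assessment. That habit is undocumented and may differ between clinicians or sites, so part of the before/after result would measure form-filling.

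If the same first plan is also the reference for agreement, the forced entries reach the overall-decision kappa and sensitivity, in a study whose stated purpose is preliminary safety evidence.

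**Working it through.** **The plan's own figures.** Data points per call: 5 + 1 from DORA and 5 + 1 from the clinician make 12; a further 5 + 1 from the clinician after clarification makes 18. Both match 8.2.5.1, and they confirm that the first clinician plan always exists. The planned 591 also reproduces from Table 7. For example, the Imperial one-stop column is 10 × 2 × 0.80 × 0.80 × 0.80 × 0.95 × 0.70 × 26 × 0.85 = 150.5. The four columns give 150.5 + 135.4 + 228.6 + 76.2 = 590.7. Nothing below disputes either figure.

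**Effect on the before/after comparison.** Let u calls be undecidable at first, of which m end as needs assessment. If undecided clinicians enter pass, m changes are recorded; if they enter needs assessment, u − m are recorded. The documents give neither u nor m. Assume u = 30 (5% of 591 = 29.6) and m = 3 (10% of 30). The same 30 calls then yield 3 or 27 recorded changes. The gap is |u − 2m|: 24 here, 0 if m = 15, and 30 if m = 0 or 30. This holds whichever plan is the reference for agreement.

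**Effect on kappa, only if the pre-clarification plan is the reference.** Assumptions, none from the documents: 30 undecidable calls; among the other 561, 10% need assessment and DORA has about 90% sensitivity and 98% specificity. In whole calls this is TP 50, FN 6, FP 10, TN 495.

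Kappa = (po − pe)/(1 − pe), where po is the observed agreement and pe the agreement expected from the margins. On the 561 decidable calls, po = 545/561 = 0.971 and pe = (60 × 56 + 501 × 505)/561² = 0.815, so kappa = 0.85.

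Now add the 30 calls. Suppose DORA flags 3 of them and the clinician always enters needs assessment. The table is TP 53, FP 10, FN 33, TN 495; po = 548/591 = 0.927; pe = (63 × 86 + 528 × 505)/591² = 0.779; kappa = 0.67. If the clinician always enters pass, the table is TP 50, FP 13, FN 6, TN 522; po = 0.968; pe = 0.819; kappa = 0.82. Varying DORA's flag rate in the 30 calls:

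| DORA flags | Kappa, default needs | Kappa, default pass | Sensitivity, default needs | Sensitivity, default pass |
|---|---|---|---|---|
| 3 (10%) | 0.67 | 0.82 | 53/86 = 0.62 | 50/56 = 0.89 |
| 15 (50%) | 0.78 | 0.73 | 65/86 = 0.76 | 50/56 = 0.89 |
| 27 (90%) | 0.87 | 0.66 | 77/86 = 0.90 | 50/56 = 0.89 |

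The order of the two defaults reverses between the first row and the second. Other accuracy assumptions move the level as well. With 5% of calls undecidable, DORA sensitivity 0.95 and specificity 0.90, 10% needing assessment, and DORA flagging undecidable calls at its overall rate (0.10 × 0.95 + 0.90 × 0.10 = 18.5%), kappa is 0.53 (default needs) or 0.59 (default pass), against 0.62 with no undecidable calls.

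**Which plan is the reference?** Section 8.2.5.1 calls the masked clinician decision, based on the call, the gold standard, but does not say whether that is before or after clarification. The ending of `supervisoroutcomeupdate` suggests the updated plan. However, `doraoutcomeupdate` has the same ending, and the protocol gives DORA no second decision, so the name does not settle the matter.

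**The case against.** The plan asks for an action, and a clinician who cannot clear a patient may regard needs assessment as a true answer. A binary action endpoint with information sufficiency measured separately is a defensible design. Insufficiency is in fact measured separately: whether clarification was needed is part of the primary outcome in Table 5, and reasons are logged. This much stands, and it limits the point. It does not supply a completion rule for the first plan, and a consistent default would be a systematic shift, still indistinguishable in the data from a genuine decision. The logged reason can locate affected calls but may concern only a symptom, and it cannot show what the first entry meant.

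Three stronger readings are tempting, and the documents do not support them:

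- A reader might infer that the primary reference as a whole rests on guesses. Only undecidable calls are involved, and only if the pre-clarification plan is the reference. The post-clarification plan is not forced, and the symptom comparisons have their own insufficient-information category.
- A reader might infer that the form hides DORA passing a patient on whom the clinician could not yet decide. Crossing DORA's recorded decision with the logged reason largely recovers this; what is missing is a planned table.
- A reader might infer that forced entries must lower agreement, or that one default is the cautious one. The table above shows that the direction depends on DORA's flag rate in those calls, which is unknown.

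**Conclusion.** The point holds in a limited form. The clinician's first management plan lacks a category for a state that the protocol itself foresees, and in those calls the before value is a forced binary entry. The before/after clarification result is exposed under any reading of the documents. With 30 undecidable calls, 3 of them ending as needs assessment, the recorded number of changes is 3 or 27 according to the clinician's habit.

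The exposure of the overall-decision kappa and sensitivity is conditional on the pre-clarification plan being the reference. If the post-clarification plan is used, the effect on kappa largely disappears. Under the first reading and the assumptions shown, kappa lies between about 0.66 and 0.87, against 0.85 on the decidable calls alone. These figures show sensitivity to unknown inputs and are not an estimate of bias.

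**What to change.** 1. In Protocol 8.2.5.1, add an insufficient-information option to the clinician's first management-plan record only. DORA's output stays binary; a third DORA category would alter the device's output and is not needed here.
2. In the SAP, state whether the reference for the overall decision is the plan before or after clarification, and define both variables ending in update.
3. In the SAP, report clarification results in four groups: undecided to pass, undecided to needs assessment, changed, and unchanged. Tabulate DORA's decision for the undecided calls. For calls already made, use the logged reasons to identify them and label that analysis as retrospective.
4. If the pre-clarification plan is the reference, give kappa and sensitivity on decidable calls, together with the two extreme allocations of the undecided calls.

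The cost is one extra code and one extra table. Under item 4, some calls also leave the headline kappa, which is why the two extreme allocations should accompany it.

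### The before/after clarification plans feed a hypothesis test whose favourable answer is a non-significant result; directional change rates with exact intervals should replace it

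*Protocol*

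**What the plan says.** Protocol 8.2.5.1 (Primary Outcomes) has a sub-heading on DORA's ability to gather sufficient information. There, "the necessity for the clinician to ask clarifying questions will be assessed". On what happens in such a call: "If clarifying points are necessary for the clinician to make a decision, the clinician will ask the necessary questions", and the clinician then records updated symptom and management decisions. The yield is stated: "Either 12 or 18 data points will be collected from each call depending on if clarifying questions are asked". The six extra items are the clinician's five symptom decisions and one plan after clarification. The intended use follows: "This will allow us to test the hypothesis that clarifying questions affect the clinical management plans (see Table 5".

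Table 5 names agreement as the only primary outcome. One of its two measures is "Whether or not the clinician had to interrupt the call to ask clarifying questions".

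Protocol 8.2.5.2 (Feasibility) adds an all-calls measure: "Proportion of autonomous calls that were completed without needing any intervention from the supervising clinician". Where clarification was prompted by insufficient information, "the clinician's management plan before and after clarifying questions will be captured to see if clarifying questions changed the management plan".

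Protocol 8.5.1 plans a kappa statistic and a comparison with hospital records. The SAP lists kappa, accuracy, the two-by-two counts, sensitivity, specificity and AUC, with one overall outcome variable for DORA and one for the supervisor. Neither mentions a comparison of plans before and after clarification.

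**The concern.** The hypothesis is that clarification affects the plan, so its null is that clarification makes no difference, which is the answer favourable to DORA. A test cannot establish its own null. Non-rejection may mean that plans seldom changed, that few calls were clarified, or that changes in the two directions offset each other.

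The clinician's decision from the call is the gold standard for agreement. DORA and the clinician can therefore agree on a pass while both lack a key fact, and kappa will not show it. The change in the clinician's plan after clarification is the within-call evidence on that failure. The case of most interest is a patient whom DORA passed, whom the clinician also passed before clarification, and whom the clinician then moved to needing assessment. A p-value for a net shift neither counts those patients nor bounds their rate.

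**Working it through.** **1. Is the test sized anywhere?** The only statistical sample size is 520 (protocol 8.3.2.1: population 1014, 95% confidence, 3% margin of error). It is a precision calculation for one proportion at p = 0.5 with finite-population correction:

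- n0 = 1.96² × 0.25 / 0.03² = 1067.1
- n = 1067.1 / (1 + 1066.1/1014) = 520.2

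The figure reproduces, but it concerns a proportion over all calls, not before/after pairs in clarified calls.

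**2. How many pairs?** Only clarified calls give a before and an after plan. The documents give no clarification rate. I assume 10%, 20% and 30% of the planned 591, which gives 59, 118 and 177 calls.

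**3. What would the usual test do?** The protocol names none. For paired binary plans I assume exact two-sided McNemar at 0.05. With m changed plans, k in one direction, p = 2 × P(Bin(m, 0.5) ≤ min(k, m − k)), capped at 1.

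- Five changes, all one way: 2 × 0.5⁵ = 0.0625
- Six changes, all one way: 2 × 0.5⁶ = 0.031

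Up to five changed plans can never be significant, however many calls were clarified.

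**4. Power.** This is the sum over m of P(m changed out of n) × P(p ≤ 0.05 given m). The change rates are assumptions, as shares of clarified calls.

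| Pass to assessment | Assessment to pass | n = 59 | n = 118 | n = 177 |
|---|---|---|---|---|
| 5% | 0% | 0.07 | 0.54 | 0.88 |
| 5% | 2% | 0.03 | 0.13 | 0.23 |
| 10% | 0% | 0.55 | 0.98 | 1.00 |
| 10% | 2% | 0.27 | 0.66 | 0.86 |
| 10% | 5% | 0.09 | 0.22 | 0.33 |
| 10% | 10% | 0.02 | 0.03 | 0.03 |

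In the last row one plan in five changes, yet the test almost never rejects, because it addresses net shift and not change.

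**5. The literal alternative.** If the null is that no plan ever changes, one change refutes it. At a 2% change rate, the chance of at least one change is 1 − 0.98ⁿ = 0.70, 0.91 and 0.97 for the three sizes. That result is no more informative.

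**6. What estimation gives from the same data** (Clopper-Pearson 95% intervals, illustrative counts):

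- 5 of 591 calls: 0.8% (0.3% to 2.0%)
- 6 of 591: 1.0% (0.4% to 2.2%)
- 12 of 591: 2.0% (1.1% to 3.5%)
- 5 of 59 clarified calls: 8.5% (2.8% to 18.7%)
- 5 of 118 clarified calls: 4.2% (1.4% to 9.6%)

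Five changes in one direction, which McNemar cannot call significant, still give a usable upper limit of 2.0% of all calls.

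**The case against.** A reader might infer that evidence in DORA's favour on this outcome can come only from a non-significant result. The documents do not support that. Table 5 records on every call whether the clinician had to interrupt, and the feasibility outcome is the share of calls completed without intervention. A high share would be favourable with no test at all. These measures do not, however, show whether clarification altered the plan, or which way.

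A reader might also infer that the clarified calls are a small subset and that the test would usually miss a relevant effect. No clarification rate is given, and the table in the working shows good power when clarification is common and changes run one way (0.98 with 118 calls and 10% against none).

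Nor does any rule make non-significance the criterion for sufficiency. The hypothesis is one sentence, absent from 8.5.1 and the SAP, and 8.2.5.2 treats the same data descriptively. That stands. But the sentence is then the only inferential use stated for these plans, and otherwise no analysis of them is specified.

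Finally, both plans are the clinician's. A change from pass to assessment does not show that DORA would have passed that patient. This too stands, and it is why the table needs DORA's decision. The reverse change can also signal missing information: the plan has only two options, so a clinician who is unsure may choose assessment first.

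**Conclusion.** The point holds for the before/after hypothesis, not for the whole sufficient-information component. As written, that hypothesis yields either a p-value whose favourable value is uninformative, or, if the SAP is followed, no before/after result. Under the assumed clarification shares and change rates, McNemar power runs from about 2% to nearly 100%. Those shares and rates, and the choice of McNemar, are assumptions; the documents supply none of them. What does not depend on the assumed rates is that McNemar measures net shift, that five or fewer changes cannot reach 0.05 with it, and that no bound or sizing is stated. This merits a change before analysis because a better summary is available from data already planned. The status of the component also needs reconciling: it sits under Primary Outcomes, while Table 5 and the SAP list only agreement as primary.

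**What to change.** In protocol 8.2.5.1, replace the sentence about testing the hypothesis with an estimation statement, and add one table to the SAP:

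- number and proportion of analysed calls needing clarification;
- number and proportion of calls in which the clinician's plan changed after clarification, over clarified calls and over all analysed calls;
- changes split into pass to needs assessment and needs assessment to pass, each cross-classified by DORA's own decision;
- exact 95% confidence intervals throughout.

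Base any statement that DORA gathers sufficient information on these rates and their upper limits, chiefly for pass-to-assessment changes where DORA also passed the patient, and not on a non-significant p-value. If the sponsor wants a pass/fail statement, the acceptable upper limit must be set before the data are seen; the documents give none. State whether the component is primary or secondary, consistently in 8.2.5.1, Table 5 and the SAP.

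The SAP needs separate clinician-plan variables for before and after clarification, because it names only one supervisor outcome. The cost is one sentence, one table and the loss of a p-value. No new data are needed.
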